10.4.1.1 Summary Statistics

Mean change and mean percentage (%) change from baseline at end of trial will be presented for each vital signs variable. In addition, descriptive statistics, i.e., the number of subjects with data, mean (standard deviation), median, minimum, and maximum values, will be presented for observed values and change from baseline at each time-point for each vital signs variable.

10.4.1.2 Data Listings

Data listings will be prepared by centre for all subjects with any abnormal vital signs value at any time-point (including screening, baseline).

10.4.2 ECGs

The 12-lead ECG will be recorded prior to randomization at cycle -1 (visit 4), at cycles 4 and 8. Results at randomization will be used as baseline. The ECG will be recorded with a calibrated ECG device after the subject has been in supine position for at least 5 minutes.

The parameters to be assessed are heart rate, PR interval, RR interval, QRS interval, QT interval and QTcF interval (i.e. QT correction according to the Fridericia's formula QTcF= $QT/RR^{0.33}$, calculated automatically in the e-CRF). ECG recordings will capture at least four QRS complexes, i.e. 3 evaluable RR intervals. The investigator will evaluate whether the ECG is normal or abnormal and if abnormal, whether it is clinically significant. ECG may be repeated for quality reasons and in this case the repeated assessment will be used for analysis.

10.4.2.1 Summary Statistics

Descriptive statistics, i.e., the number of subjects with data, mean (standard deviation), median, minimum, and maximum values, will be presented for observed values and change from baseline at each time-point for each ECG variable.

10.4.2.2 Data Listings

Data listings will be prepared by treatment and site for all subjects with any abnormal ECG value at any time-point.

10.5 Other Safety Variables

10.5.1 Changes in Bone-turnover Markers

Changes in bone-turnover markers will be summarised.

10.5.2 Echocardiography

The proportion of subjects with clinically significant echocardiography findings will be tabulated by treatment.

10.5.3 Impulsive-Compulsive Disorders

Frequency-tables for each item of the questionnaire for impulsive-compulsive disorders as well as the proportion of subjects having potential behaviours associated with impulse control disorders will be summarized by treatment.

Treatment-emergent adverse events potentially related to behaviours associated with impulse control disorder will be summarised, similar to the tables described in 10.2.2. An AE is considered to potentially related to behaviours associated with impulse control disorder if the PT is included in the SMQ hostility/aggression (broad) or included in the list of PTs below:

Alcohol abuse Alcohol problem Alcohol use Behavioural addiction Binge drinking Binge eating Compulsions Compulsive hoarding Compulsive sexual behaviour Compulsive shopping Disturbance in sexual arousal Dopamine dysregulation syndrome Drug abuse Drug abuser Eating disorder Economic problem Emotional disorder **Emotional distress**

Euphoric mood Excessive masturbation Exhibitionism Gambling Gambling disorder Gaming disorder High risk sexual behaviour Hyperphagia Hypersexuality Increased appetite Judgement impaired Kleptomania Libido disorder Libido increased Male orgasmic disorder Mental disorder Mental status changes Mood altered Mood swings Obsessive rumination

Obsessive thoughts Obsessive-compulsive disorder Obsessive-compulsive personality disorder Obsessive-compulsive symptom Overconfidence Poriomania Promiscuity Pseudologia Restlessness Self-esteem inflated Sexual activity increased Sexually inappropriate behaviour Stereotypy Thinking abnormal Weight increased

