#### **Stopping Criteria (Discontinuation from Treatment)**

#### Stopping Criteria on Subject Level

Subjects will be discontinued from the treatment if any of the following stopping criteria are met:

- Any significant changes in valvular regurgitation or stenosis from baseline associated with clinical signs and symptoms
- Any clinically significant abnormal ECG finding defined as prolongation of QTcF ≥500 msec or change from baseline QTcF value of ≥60 msec confirmed by the central cardiac laboratory
- Treatment-related syncope (orthostatic collapse associated with an abrupt, transient, complete loss of consciousness and inability to maintain postural tone, with rapid and spontaneous recovery) incompatible with continuing treatment
- Treatment-related alteration in consciousness or mental status (such as confusion, amnesia, loss of alertness and disorientation) incompatible with continuing treatment
- Treatment-related pathological behaviors of impulse control disorders including pathological gambling, compulsive buying, binge eating, and hypersexuality (see section 7.2.2.10) incompatible with continuing treatment
- Treatment-related acute psychosis, e.g. hallucinations/delusion

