## 7.2.2.10 Impulse Control Disorder

A questionnaire adapted from a validated Questionnaire for Impulsive-Compulsive Disorders in Parkinson's Disease-Rating Scale will be used to monitor any significant signs of pathological behaviors associated with impulse control disorder during the trial. The questionnaire has four primary questions concerning thoughts, urges/desires, behavior controls and engagement, each of which is applied to various behaviors associated with impulse control disorders, i.e. gambling, sex, buying, eating, performing tasks or hobbies, repeating simple activities and medication use. However, the original sub-question on medication use is not appropriate for this trial, as it focuses on the medication used for Parkinson's disease. Therefore this sub-question "taking your Parkinson's disease medications" has been deleted (see Appendix 1). The questionnaire uses a 5-point Likert scale (score 0-4) to measure the frequency of behaviors (never, rarely, sometimes, often and very often).

The questionnaire will be completed by trained trial coordinators based on subjects' verbal responses on an electronic tablet prior to randomization at cycle -1 (visit 4) and prior to other non-

PRO procedures at cycle 4 (visit 10). Subjects will be asked to answer questions based on behaviors occurring in any 4-week period during the trial at designated visits. An instruction sheet will be provided to trial coordinators with examples of the specific behaviors being assessed and a brief description of the Likert scale categories for frequency. Subjects indicating a score  $\geq 2$  for any subquestions of Question 3 or a score  $\geq 1$  for any sub-questions of Question 4, i.e. a frequency of "sometimes" or even higher for any sub-questions of Question 3 regarding "Difficulty in controlling behaviors" or a frequency of "rarely" or even higher for any sub-questions of Question 4 regarding "Engage in activities", will be considered having potential behaviors associated with impulse control disorders. The behavior identified will be reported as an adverse event. In addition, if this is considered to be treatment-related by the investigator, the subject will be discontinued from the treatment (see section 3.6.7) and, if needed, will be referred to psychiatric counselling and will be followed up until symptoms are resolved.

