## 7.2.2.11 Adverse Events

Adverse events will be recorded from the signing of informed consent(s) for participation in the trial until the end-of-trial visit. For each adverse event, the following parameters will be recorded by the investigator on the Adverse Event Log: description of event, date and time of onset, intensity, causal relation to IMP, action taken to IMP, other actions taken, seriousness of the adverse event, date and time of outcome, and outcome. A search for predefined preferred terms and reported terms will be conducted on all treatment-emergent adverse events to identify those potentially related to behaviors associated with impulse control disorders. See section 8.

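### SAP 10.5.3 selects impulse-control adverse events by coded preferred term only, without declaring that the protocol's search of reported terms has been dropped

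*SAP*

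**What the plan says.** Protocol 7.2.2.11 sets the search rule for impulse-control events: "A search for predefined preferred terms and reported terms will be conducted on all treatment-emergent adverse events to identify those potentially related to behaviors" of that kind. It names two sources, the coded term and the term as reported.

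Protocol 7.2.2.10 adds a second route into the adverse event data. When a woman's answers reach the questionnaire threshold, "The behavior identified will be reported as an adverse event". The threshold is a score of 2 or more on any part of Question 3, or 1 or more on any part of Question 4.

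SAP 10.5.3 plans three outputs: item frequencies from the questionnaire, the proportion of women with potential impulse-control behaviours, and a table of treatment-emergent adverse events potentially related to such behaviours. The rule for entering that table is: "An AE is considered to potentially related to behaviours associated with impulse control disorder if the PT is included in the SMQ". The query meant is the broad one for hostility and aggression; the only other way in is to be coded to a term on a printed list. The table follows the format of SAP 10.2.2, that is, by system organ class and preferred term. SAP section 12, on deviations from the protocol analysis, says nothing about this search.

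**The concern.** The protocol uses two nets and the SAP uses one. Reported terms matter because the preferred term is assigned afterwards: protocol 8.1 has all events coded in MedDRA by the sponsor, and protocol 8.2.2 has sites record separate signs and symptoms when there is no diagnosis. A search of reported terms guards against an impulse-control behaviour being coded to something the list does not contain.

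The topic is not incidental. Symptoms of impulse control disorders are named in the safety objective, and protocol 3.6.7 makes "Treatment-related pathological behaviors of impulse control disorders including pathological gambling, compulsive buying, binge eating, and hypersexuality" a subject-level reason to stop treatment when incompatible with continuing. A reader of the trial report will take the impulse-control table as the result of the protocol's search. As planned, it is the result of a narrower one, and nothing tells the reader so.

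**Working it through.** No sample size, power or event figure is involved, so there is no plan figure to reproduce. The check compares the texts.

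**1. The two rules**

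| | Protocol 7.2.2.11 | SAP 10.5.3 |
|---|---|---|
| Events searched | all treatment-emergent | treatment-emergent |
| Preferred term | yes, predefined | yes: one broad MedDRA query plus a printed list |
| Reported term | yes | no |

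The printed list has 18 + 20 + 15 = 53 distinct terms.

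**2. Direction of the error.** Let P be the events whose preferred term is in the query or on the list, and R the events whose reported term points to an impulse-control behaviour. Read naturally, the protocol selects P or R; the SAP selects P. The difference is the events in R but not in P. Dropping R can only remove events from the table.

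**3. Can an event be in R but not in P?** The questionnaire covers gambling, sex, buying, eating, tasks or hobbies, and repeating simple activities. The first four have direct matches on the list (for example Gambling disorder, Hypersexuality, Compulsive shopping, Binge eating). No printed term names tasks or hobbies, and none reads impulse-control disorder or impulsive behaviour. Whether the broad query covers these cannot be checked from the documents. The Question 4 threshold is also low: an answer of rarely is enough. So a flagged behaviour coded outside P is possible; the documents do not show how often it would happen.

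**4. Consistency within SAP 10.5.3.** A woman who reaches the threshold during treatment counts in the questionnaire proportion. Her behaviour must also be entered as an adverse event, but no SAP rule carries that event into the impulse-control table unless its preferred term is in P. She can therefore appear in one output and not in the other, purely through coding.

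**5. Is the change declared?** Section 12 lists no interim analysis, no statistical analysis, no shift or markedly-abnormal tables, and no summary of the progesterone proportion or biomarkers. The reported-term search is not there. The reason given for those omissions, low numbers, is not offered here, and a text search is easier with few events.

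**6. Scale.** One woman left out lowers a column's percentage by 100/n points. At the planned 70 per group that is 100/70 = 1.4 points. Actual column sizes are not given. If they were 10 to 20 (an assumption; SAP section 1 says only that recruitment was low), it would be 100/20 = 5 to 100/10 = 10 points. These are values per omitted woman, not estimates of how many are omitted.

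**The case against.** The strongest reply is that the search only groups events already recorded, so nothing is lost from the data. SAP 10.2.2 tabulates all treatment-emergent events and lists all events by preferred term. The questionnaire proportion, which is the declared secondary endpoint, is tabulated separately. Events leading to withdrawal get their own table, listing and narrative. The stopping criterion is applied to each subject during the trial and does not depend on this table. No document shows a flagged behaviour being coded outside the list. Reporting is descriptive, so no test is affected. The SAP draws on protocol versions 4.0, 5.0 and 6.0, with 5.0 the basis for the report, and only 6.0 is at hand.

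All of this stands, and it limits the consequence. It does not remove the discrepancy: a listing lets someone look for missed events, but it does not carry out the search the protocol promised.

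A reader might infer more. The list includes terms such as those ending in "Stereotypy Thinking abnormal Weight increased", and the run "Male orgasmic disorder Mental disorder Mental status changes Mood altered Mood swings", one of them male-only in a trial of women. It is tempting to say that the table is swamped by unrelated events and cannot show true ones. The documents do not support that. Each preferred term has its own row, so a case of weight gain is visible as weight gain and a gambling disorder as a gambling disorder. The protocol leaves the choice of terms open and aims at events only potentially related, for which a wide list is reasonable; eating is among the behaviours assessed, so appetite and weight terms can be defended. The male-only term should add nothing. One can compute that, if 5% of women had an unrelated event under a listed term, a column of 10 would show at least one with probability 1 − 0.95^10 = 0.40. Both the rate and the column size are assumptions, and the result is the chance of one visible row, not of a false impulse-control case.

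A reader might also infer that between questionnaires the event search is the only source. Protocol 7.2.2.10 has the questionnaire ask about any 4-week period during the trial, so it looks back beyond the visit, although it relies on recall.

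**Conclusion.** The point holds as an undeclared departure from the protocol. SAP 10.5.3 omits the reported-term half of the search in protocol 7.2.2.11, and section 12 does not say so. The impulse-control table can undercount relative to the protocol's rule and can disagree with the questionnaire proportion beside it.

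The size cannot be estimated from the documents and may be nil. The practical effect is limited by the full event tables and listings, the separate questionnaire summary and the descriptive reporting. The conclusion rests on two assumptions: that the protocol's wording means either kind of term qualifies an event, and that version 5.0 does not differ from 6.0 here, which could not be checked.

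The breadth of the term list is not an error, and the claim that the safety objective cannot be answered is not supported.

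**What to change.** In SAP 10.5.3:

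- Add a search of the reported terms of all treatment-emergent adverse events, with the search words stated in advance and the hits reviewed blind to treatment.
- Include in the table every event entered because of a positive questionnaire, whatever its preferred term.

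If the sponsor prefers to keep the coded search alone, section 12 should declare this and give the reason. That would settle the disclosure but not the possible undercount.

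The cost is a text search of reported terms already in the database and a short blinded review; no new data are needed. A separate row for the specific behaviours would be an optional convenience, since the table already shows each preferred term.

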10.5.4 Ring Acceptability

Frequency-tables for each item (as applicable) of the ring acceptability questionnaire will be presented by cycle and treatment.

11 Interim Analyses

An interim analysis with the option to stop the trial early due to futility was planned, but as the trial was prematurely discontinued, this interim analysis was not performed

The trial was terminated early. The decision was taken due to the results from the parallel phase 2 trial in Europe (Trial 000295) and the continued difficulties with subject recruitment.

Due to the low number of subjects recruited, no interim analysis was performed, and no statistical analysis was performed. Instead results are presented as descriptive statistics by treatment group separately for Part A and Part B.

Furthermore, due the low number of subject the shift tables and tables displaying proportions of subjects with markedly abnormal values for the safety endpoint will not be prepared, the information on change from baseline can be assessed using the listings.

12 Deviations from Protocol Analysis

The trial was terminated early. The decision was taken due to the results from the parallel phase 2 trial in Europe (Trial 000295) and the continued difficulties with subject recruitment.

Due to the low number of subjects recruited, no interim analysis was performed, and no statistical analysis was performed. Instead results are presented as descriptive statistics by treatment group separately for Part A and Part B.

Due the low number of subjects the shift tables and tables displaying proportions of subjects with markedly abnormal values for the safety endpoint will not be prepared, the information on change from baseline can be assessed using the listings.

Due to the low number of subjects the proportion of subjects with serum levels of midluteal progesterone ≥ 25 nmol/, and the endometriosis biomarkers will not be summarized

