## 7.4.14 Transvaginal Ultrasound

A transvaginal ultrasound will be performed by an experienced sonographer before entry into run-in (before or at visit 1), and at end-of-treatment / cycle 4 (at visit 10). The transvaginal ultrasound will

assess uterus, endometrium and ovaries to evaluate endometrial thickness, number and size of endometrioma(s), ovarian cyst(s) and fibroid(s) if presented.

Endometrial thickness (composed of both layers of the endometrium) will be measured in the sagittal view of the uterus from the proximal and distal interfaces between the echogenic endometrium and the hypoechoic inner layer of the myometrium. Care should be taken not to include the presence of any fluid in the uterine cavity in calculating the endometrial thickness value. Endometrial thickness will be recorded in mm.

Endometrioma, fibroid and ovarian cyst will be recorded as observed or not. If observed, the number and size of endometrioma(s), fibroid(s) and ovarian cyst(s) should be recorded.

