#### Physical and Gynecological Examination

Physical and gynecological examination findings at end-of-treatment compared to screening will be summarized in shift tables and all subjects with any abnormal finding will be listed by subject and time point. The list will include both screening and end-of-treatment assessment for comparison.

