#### Transvaginal Ultrasound

Endometrial thickness, number and size of fibroids if presented and number and size of ovarian cyst if presented will be tabulated by screening, RM+7 visits of cycle 4.

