7.4 Physical Examination

Subjects with abnormalities at any screening, or post-baseline visit will be listed with all physical examination evaluations.

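### The SAP omits the protocol's gynecological-examination and transvaginal-ultrasound outputs; two of the three losses are undeclared, and the fallback to listings fails for the gynecological shift table

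*SAP*

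**What the plan says.** Protocol 9.8, under Other Safety Variables, sets out the outputs. For the examinations: "Physical and gynecological examination findings at end-of-treatment compared to screening will be summarized in shift tables", and in addition "all subjects with any abnormal finding will be listed by subject and time point". For ultrasound: "Endometrial thickness, number and size of fibroids if presented and number and size of ovarian cyst if presented will be tabulated", at screening and at cycle 4.

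The SAP was written after early termination and replaces the planned inference with descriptive statistics. Sections 11 and 12 both state that "the shift tables and tables displaying proportions of subjects with markedly abnormal values for the safety endpoint will not be prepared", on the ground that "the information on change from baseline can be assessed using the listings". The only SAP text on examination findings is section 7.4: "Subjects with abnormalities at any screening, or post-baseline visit will be listed with all physical examination evaluations".

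The SAP has no section, table or listing for gynecological-examination findings or ultrasound results. In the text available, ultrasound appears only in the abbreviation key to the design diagram.

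**The concern.** A SAP may drop protocol outputs when a trial stops early, but it should say which ones and give a reason that is true for each. Section 12 exists for this purpose. It is specific enough to name the mid-luteal progesterone proportion and the endometriosis biomarkers as not summarized, yet it is silent on the gynecological listing and the ultrasound tabulation.

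The product is a vaginal ring. The scheduled gynecological examination (protocol 7.4.12) is the systematic look at the application site, covering seven categories: breast, external genitalia, vagina, cervix, uterus, adnexa and cul-de-sac. The other examination for local irritation (protocol 8.3.6) is unscheduled and follows a spontaneous complaint. Ultrasound is the only scheduled pelvic imaging, in a trial whose rationale (protocol 1.2) is lesion reduction.

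Protocol 7.4.12 grades changes in three levels, and only the clinically significant level must become an adverse event. A change to an abnormal finding without clinical significance would be collected and then appear in no output.

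**Working it through.** No formula applies. The check compares the outputs planned in protocol 9.8 with every SAP section that produces a safety table or listing.

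| Assessment | Planned in protocol 9.8 | SAP table | SAP listing with post-baseline values | Loss declared in SAP 11/12 |
|---|---|---|---|---|
| Laboratory | shift and markedly-abnormal tables, listing | 10.3.1 | 10.3.3 | yes, for the tables |
| Vital signs | as laboratory | 10.4.1.1 | 10.4.1.2 | yes, for the tables |
| Physical examination | shift table, listing | none | 7.4 | yes, for the shift table |
| Gynecological examination | shift table | none | none | yes, if the general sentence reaches it |
| Gynecological examination | abnormal-findings listing | not applicable | none | no |
| Transvaginal ultrasound | tabulation | none | none | no |

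Step 1, the fallback. For the first three assessments a listing exists, so the reason given in sections 11 and 12 can be defended. For the gynecological shift table there is no such listing. The remaining general listing, SAP 7.5, covers baseline characteristics not listed elsewhere and so cannot show change.

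Step 2, whether SAP 7.4 already includes gynecological findings. The protocol describes the physical examination in 7.4.11 and the gynecological examination in 7.4.12, with different categories; none of the seven gynecological categories is in the 7.4.11 list. SAP 7.4 uses the name of the first only.

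Step 3, ultrasound. The protocol planned a plain tabulation, neither a shift table nor a markedly-abnormal table. The sentence in sections 11 and 12 therefore neither removes it nor offers a substitute. The move to descriptive statistics does not explain its absence either, since the tabulation was already descriptive.

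Step 4, the count. Gynecological shift table, gynecological listing and ultrasound tabulation make 3 outputs. The SAP provides 0 of the 3. At most 1 (the shift table) is covered by a declared deviation, so at least 3 − 1 = 2 are missing undeclared.

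Step 5, what remains. Clinically significant gynecological changes (protocol 7.4.12) and ultrasound findings (protocol 8.1) are adverse events and enter the tables of SAP 10.2.2. SAP 10.2.3.5 tabulates vaginal irritation and infection events, all and related. SAP 10.5.4 tabulates ring acceptability by cycle and treatment. The Biberoglu and Behrman sign scores in SAP Table 9-1 carry pelvic tenderness and induration. None of these gives findings by gynecological category at screening and after treatment, or ultrasound measurements.

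**The case against.** The best defence has four parts.

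First, SAP 7.4 may be shorthand, because protocol 9.8 puts physical and gynecological examinations under one heading. This is possible. If it was meant, the gynecological listing exists, the fallback works, and only the ultrasound gap remains. The wording and the separate protocol sections point the other way, so the SAP needs to say so.

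Second, the sentence on dropped tables refers to the safety endpoint, and these examinations are not endpoints. On that reading the sentence does not reach the gynecological shift table. Its reason is then not false for that table, but all three outputs are undeclared instead of two.

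Third, these are non-endpoint descriptive outputs in a small, terminated trial, and no efficacy or safety-endpoint conclusion depends on them. That is correct and limits the weight of the point. It does not justify omitting a listing, which is the SAP's own substitute for tables when numbers are low.

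Fourth, the visit schedule. Protocol version 6.0 puts the post-treatment examinations at visit 10. SAP section 1 says most women were randomized under version 5.0, which has a Part B and different visit numbering. The examination schedule of that version is not in the documents, so no count of examinations per woman can be given.

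A reader might also infer three stronger things. One is that local ring effects go unreported; the adverse-event and acceptability tables show otherwise. Another is that the SAP says ultrasound change can be read from listings; its sentence covers only shift and markedly-abnormal tables. The third is that the SAP dropped endometrioma size. Protocol 7.4.14 requires that, where observed, "the number and size of endometrioma(s), fibroid(s) and ovarian cyst(s) should be recorded", but the table in protocol 9.8 covers only thickness, fibroids and cysts. That gap is in the protocol, and the SAP leaves it open.

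**Conclusion.** The point holds in a limited form. Followed as written, the SAP produces none of the three outputs that protocol 9.8 plans for the gynecological examination and transvaginal ultrasound. Two of them, the gynecological listing and the ultrasound tabulation, disappear without being declared. The stated reason for dropping shift tables fails for the gynecological one. The loss is the systematic examination data: findings in seven gynecological categories, including changes not judged clinically significant, plus endometrial thickness and the number and size of fibroids and ovarian cysts. It affects every woman examined at screening and again on treatment; the documents do not give that number.

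The conclusion assumes that SAP 7.4 means the physical examination only, and that the outputs in version 6.0 of the protocol, the version available, also represent what was planned for women randomized under earlier versions. The point has no bearing on type I error, power or the primary endpoint. It should be corrected because the remedy is cheap and makes the SAP's account of its deviations accurate.

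**What to change.** - Extend the SAP 7.4 listing to gynecological-examination findings at screening and post-baseline, for women with any abnormality. If 7.4 was already meant to include them, say so.
- Restore the protocol's descriptive ultrasound table (endometrial thickness, number and size of fibroids and of ovarian cysts) by treatment for Part A, and for Part B where data were collected.
- Optionally add endometrioma number and size to that table. They are collected but were never in the planned output, so this is an addition and should be labelled as one.
- Reword the sentence in sections 11 and 12 so that it points to listings only where a listing exists, and name in section 12 any planned output that is still omitted.

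The cost is one listing, one descriptive table and a few lines of text, all from data already collected.
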